10.7.1. Definition of AE and ADE

AE and ADE Definition

• An AE is defined as any untoward medical occurrence, unintended disease or injury, or untoward clinical signs (including abnormal laboratory finding) in study participants, users, or other persons, whether or not related to the investigational medical device. This definition includes events related to the investigational medical device or comparator for study participants, users, and other persons. This definition also includes events considered related to procedures for study participants only.• An ADE is defined as an adverse event related to the use of an investigational medical device. This definition includes any adverse events resulting from insufficient or inadequate instructions for use, deployment, implantation, installation, or operation, or any malfunction of the investigational medical device as well as any event resulting from use error or from intentional misuse of the investigational medical device.

10.7.2. Definition of SAE, SADE, and Unanticipated Serious Adverse Device Effect

If an event is not an AE per definition above, then it cannot be an SAE even if serious conditions are met (eg, hospitalization for signs/symptoms of the disease under study, death due to progression of disease).

An SAE is an AE that:
a. Led to death.
b. Led to serious deterioration in the health of the participant, that either resulted in: 
• A life-threatening illness or injury. The term “life-threatening” in the definition of serious refers to an event in which the participant was at risk of death at the time of the event. It does not refer to an event, that hypothetically might have caused death, if it were more severe.• A permanent impairment of a body structure or a body function.• Inpatient or prolonged hospitalization. Planned hospitalization for a preexisting condition, or a procedure required by the protocol, without serious deterioration in health, is not considered an SAE.• Medical or surgical intervention to prevent life-threatening illness or injury or permanent impairment to a body structure or a body function.
c. Led to fetal distress, fetal death, or a congenital abnormality or birth defect.
SADE Definition

• An SADE is defined as an adverse device effect that has resulted in any of the consequences characteristic of a serious adverse event.
USADE Definition

• A USADE is a serious adverse device effect which by its nature, incidence, severity, or outcome has not been identified in the current version of the risk analysis management file.

10.7.3. Definition of Device Deficiency

Device Deficiency Definition

• A device deficiency is an inadequacy of a medical device with respect to its identity, quality, durability, reliability, safety, or performance. Device deficiencies include malfunctions, use errors, and inadequate labeling.

10.7.4. Recording/Reporting and Follow-up of AEs and/or SAEs and Device Deficiencies

AE, SAE, and Device Deficiency Recording

• When an AE/SAE/device deficiency occurs, it is the responsibility of the injection administrator/trainer to review all documentation (eg, hospital progress notes, laboratory reports, and diagnostic reports) related to the event.• The injection administrator/trainer will then record all relevant AE/SAE/device deficiency information in the participant's medical records, in accordance with the investigator's normal clinical practice and on the appropriate form of the CRF.• It is not acceptable for the injection administrator/trainer to send photocopies of the participant's medical records to Pfizer Safety in lieu of following the reporting process described in the IP Manual.• There may be instances when copies of medical records for certain cases are requested by Pfizer Safety. In this case, all participant identifiers, with the exception of the participant number, will be redacted on the copies of the medical records before submission to Pfizer Safety.• The investigator will attempt to establish a diagnosis of the event based on signs, symptoms, and/or other clinical information. Whenever possible, the diagnosis (not the individual signs/symptoms) will be documented as the AE/SAE.• For device deficiencies, it is very important that the investigator describes any corrective or remedial actions taken to prevent recurrence of the incident.
• A remedial action is any action other than routine maintenance or servicing of a medical device where such action is necessary to prevent recurrence of a device deficiency. This includes any amendment to the device design to prevent recurrence.
Assessment of Intensity

The investigator will make an assessment of intensity for each AE/SAE/device deficiency reported during the study and assign it to 1 of the following categories:
 
• Mild: An event that is easily tolerated by the participant, causing minimal discomfort and not interfering with everyday activities.• Moderate: An event that causes sufficient discomfort and interferes with normal everyday activities.• Severe: An event that prevents normal everyday activities. An AE that is assessed as severe should not be confused with an SAE. Severe is a category utilized for rating the intensity of an event; and both AEs and SAEs can be assessed as severe.

- An event is defined as “serious” when it meets at least 1 of the predefined outcomes as described in the definition of an SAE, NOT when it is rated as severe.

Assessment of Causality

- The investigator is obligated to assess the relationship between study intervention and each occurrence of each AE/SAE/device deficiency.
- A “reasonable possibility” of a relationship conveys that there are facts, evidence, and/or arguments to suggest a causal relationship, rather than a relationship cannot be ruled out.
- The investigator will use clinical judgment to determine the relationship.
- Alternative causes, such as underlying disease(s), concomitant therapy, and other risk factors, as well as the temporal relationship of the event to study intervention administration will be considered and investigated.
- The investigator will also consult the product information, for marketed products, in his/her assessment.
- For each AE/SAE/device deficiency, the investigator **must** document in the medical notes that he/she has reviewed the AE/SAE/device deficiency and has provided an assessment of causality.
- There may be situations in which an SAE has occurred and the investigator has minimal information to include in the initial report to the sponsor. However, it is very important that the investigator always make an assessment of causality for every event before the initial transmission of the SAE data to the sponsor.
- The investigator may change his/her opinion of causality in light of follow-up information and send an SAE follow-up report with the updated causality assessment.
- The causality assessment is one of the criteria used when determining regulatory reporting requirements.

Follow-up of AE/SAE/Device Deficiency

- The investigator is obligated to perform or arrange for the conduct of supplemental measurements and/or evaluations as medically indicated or as requested by the sponsor to elucidate the nature and/or causality of the AE/SAE/device deficiency as fully as possible. This may include additional laboratory tests or investigations, histopathological examinations, or consultation with other healthcare providers.

- If a participant dies during participation in the study or during a recognized follow-up period, the investigator will provide Pfizer Safety with a copy of any postmortem findings including histopathology.
- New or updated information will be recorded in the originally completed CRF.
- The investigator will submit any updated SAE data to the sponsor within 24 hours of receipt of the information.

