- The investigator should assign the responsibility of the injection administrator/trainer to a member of the study site staff who will not participate in any other study-related activities, ensuring that all other site staff do not risk becoming accidentally unblinded. Contact between the injection administrator/trainer and study participants should be kept to a minimum. The injection administrator/trainer must not take any action that may potentially reveal treatment assignment to the participant or site staff. The investigator, site staff, and any study participants other than the injection administrator/trainer must not be allowed to know the study intervention assigned to any study participant and must not be allowed to see the treatment records.

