6.4.2. Dupilumab Compliance

There are viscosity differences between dupilumab and the matched placebo, and as such there is a potential for the administrator/trainer who may have previous experience administering dupilumab to notice this difference in viscosity. Although no injection administrator/trainer will know the treatment allocation of participants, as a risk mitigation against accidental unblinding affecting study integrity this injection administrator/trainer will only administer injectable study intervention, or observe/train participants administering injectable study intervention, and will account/reconcile any unused syringes returned by participants, will be isolated from all other study activities, and will be treated as if unblind. Throughout the protocol, these individuals will be referred to as "injection administrator/trainer" in order to make this clear distinction from other site personnel.

When injectable study intervention is administered at the research facility, it will be administered under the supervision of the injection administrator/trainer only.

If the participant is unwilling/unable to self-administer the injectable study intervention or arrange for a caregiver to administer the injectable study intervention, then it is permissible for the site to arrange for the participant to return to the site for administration by the injection administrator/trainer.

Participants will be directed to bring any used and unused syringe cartons to visits following administration at home. Study sites will provide participants with a sharps container for disposal of used syringes. Participants will return this sharps container to the study site at the final visit for disposal.

If an injectable dose is missed, participants (or caregivers, if applicable) should be instructed to administer the injection within 7 days from the missed dose and then resume the participant's original schedule. If the missed dose is not administered within 7 days, participants (or caregivers, if applicable) should be instructed to wait until the next dose on the original schedule.

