10.3.3. Recording/Reporting and Follow-Up of AE and/or SAE

AE and SAE Recording/Reporting

The table below summarizes the requirements for recording adverse events on the CRF and for reporting serious adverse events on the Clinical Trial (CT) Serious Adverse Event (SAE) Report Form to Pfizer Safety. These requirements are delineated for 3 types of

events: (1) SAEs; (2) non-serious adverse events (AEs); and (3) exposure to the study interventions during pregnancy or breastfeeding, and occupational exposure.

It should be noted that the CT SAE Report Form for reporting of SAE information is not the same as the AE page of the CRF. When the same data are collected, the forms must be completed in a consistent manner. AEs should be recorded using concise medical terminology and the same AE term should be used on both the CRF and the CT SAE Report Form for reporting of SAE information.

Safety Event	Recorded on the CRF	Reported on the CT SAE Report Form to Pfizer Safety Within 24 Hours of Awareness
SAE	All	All
Non-serious AE	All	None
Exposure to the study intervention during pregnancy or breastfeeding, and occupational exposure	All AEs/SAEs associated with exposure during pregnancy or breastfeeding Occupational exposure is not recorded.	All (And exposure during pregnancy [EDP] supplemental form for EDP) Note: Include all SAEs associated with exposure during pregnancy or breastfeeding. Include all AEs/SAEs associated with occupational exposure.

- When an AE/SAE occurs, it is the responsibility of the investigator to review all documentation (eg, hospital progress notes, laboratory reports, and diagnostics reports) related to the event.
- The investigator will then record all relevant AE/SAE information in the CRF.
- It is **not** acceptable for the investigator to send photocopies of the participant’s medical records to Pfizer Safety in lieu of completion of the Pfizer Safety /AE/SAE CRF page.
- There may be instances when copies of medical records for certain cases are requested by Pfizer Safety. In this case, all participant identifiers, with the exception of the participant number, will be redacted on the copies of the medical records before submission to Pfizer Safety.
- The investigator will attempt to establish a diagnosis of the event based on signs, symptoms, and/or other clinical information. Whenever possible, the diagnosis (not the individual signs/symptoms) will be documented as the AE/SAE.

Assessment of Intensity

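### Section 10.7.4 has the injection administrator/trainer review clinical records and record AE/SAE information, contrary to the isolation rule in Sections 6.1.1.2 and 6.4.2

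*Protocol*

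**What the plan says.** **The isolation rule.** Protocol Section 6.4.2 acknowledges that dupilumab and its placebo differ in viscosity, so an experienced injector might notice which one is in the syringe. As mitigation, "this injection administrator/trainer will only administer injectable study intervention, or observe/train participants administering injectable study intervention". The only task added to those is accounting for returned unused syringes. The person "will be isolated from all other study activities, and will be treated as if unblind". Section 6.1.1.2 says the same: the role goes "to a member of the study site staff who will not participate in any other study-related activities".

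**The Appendix 7 instruction.** Section 10.7.4 opens with "When an AE/SAE/device deficiency occurs, it is the responsibility of the injection administrator/trainer to review all documentation", and its examples include hospital notes, laboratory reports and diagnostic reports. It continues: "The injection administrator/trainer will then record all relevant AE/SAE/device deficiency information in the" participant's medical records and on the CRF.

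**The general AE route.** Section 8.3 makes the investigator and qualified designees responsible for detecting and recording AEs and SAEs. Section 8.3.1.2 has the investigator enter them on the CRF. Appendix 3, Section 10.3.3, states: "When an AE/SAE occurs, it is the responsibility of the investigator to review all documentation".

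**The concern.** The isolation rule exists because the double-dummy is imperfect at the syringe. It works only if the person who may notice the difference sees no outcome data and writes nothing that blinded staff will read. Section 10.7.4 asks that person to do both.

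What is at stake is mainly the safety comparison, which is a stated objective of the trial (Section 3). The protocol's own background describes events that could confirm a guess: injection-site reactions and conjunctivitis were more frequent with dupilumab than with placebo (Section 2.2.2), and platelet counts fell in a dose-dependent way with abrocitinib (Section 2.2.3). Someone who has noticed the viscosity and then reads laboratory and clinical reports has more to go on. If that person also writes the event into the chart, the wording can carry a cue, because blinded site staff can be expected to consult the chart. Appendix 2 takes the same risk seriously elsewhere: laboratory results that could unblind are withheld from sites.

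There is also an operational problem. Two roles are each told to review and record the same kind of event.

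**Working it through.** No figure is attached to this point, so the check is a comparison of texts.

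1. **Duties allowed.** Section 6.4.2 gives a closed list: administer, observe or train, reconcile syringes. Section 6.1.1.2 excludes all other study activity. Neither mentions device-event reporting, review of clinical records, or CRF entry of adverse events.

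2. **Duties assigned elsewhere to the same person.**
   - Section 8.3.9: detect and document device incidents and malfunctions.
   - Section 8.3.9.1: notify the sponsor of deficiencies learned of after a participant leaves the study.
   - Section 8.3.9.2: ensure follow-up, including supplemental investigation of what a deficiency was and what caused it.
   - Sections 8.3.9.3 and 8.3.9.4: report deficiencies to the sponsor, and comply with local requirements for reporting to the ethics committee.
   - Section 10.7.4: review clinical documentation; record AE, SAE and device deficiency information in the chart and CRF.

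   None of these is on the list in step 1.

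3. **Does a device-only reading remove the conflict?** Appendix 7 says that its procedures apply to the sponsor's devices, which Section 6.1.2 identifies as the prefilled syringes. Suppose, then, that 10.7.4 covers syringe events only. The administrator/trainer would still read clinical reports and write in the chart and CRF for those events, and the closed list allows neither. The conflict remains, with a narrower reach.

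4. **Does 10.7.4 state that narrower reach?** It does not. Its wording joins AEs, SAEs and device deficiencies without restriction, and the AE definition in Section 10.7.1 applies "whether or not related to the investigational medical device". The breadth is therefore ambiguous in the protocol itself.

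5. **Who owns the record?** The review and recording bullets in 10.7.4 closely follow those in 10.3.3, with the injection administrator/trainer in place of the investigator. A syringe fault that comes with an AE also goes through Appendix 3, by the note in Section 8.3.9. Both roles are then told to review the documentation and enter it on the CRF.

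6. **What stays with the investigator inside Appendix 7.** Diagnosis, intensity, causality, and the supplemental evaluations under follow-up. That last item overlaps with Section 8.3.9.2, which gives supplemental investigation of deficiencies to the administrator/trainer.

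7. **A related mismatch.** Section 6.1.2 assigns detection and reporting of syringe incidents to the investigator and points to Section 8.3.6. That section is headed cardiovascular and death events and is marked not applicable. Section 8.3.9 assigns the same task to the administrator/trainer.

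**The case against.** The strongest defence reads the protocol as a whole. Section 8.3 sends AE and SAE definitions to Appendix 3 and device-related events to Appendix 7. Section 8.3.1.2 has the investigator enter AEs on the CRF, and Section 8.3.2 refers the recording method to Appendix 3. Section 8.3.9 gives the administrator/trainer only device incidents and malfunctions. On this reading ordinary AEs never reach that person, and 10.7.4 is loosely worded text in a device appendix. Other safeguards also stand: Section 6.4.2 says that no administrator/trainer will know the allocation, Section 6.1.1.2 forbids any action that might reveal it, and the investigator judges diagnosis, intensity and causality.

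Most of this is right, and it limits the consequence. It does not remove the contradiction, because even the device-only version asks for tasks that the closed list excludes.

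It does dispose of several stronger inferences that a reader might draw:

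- **That the blind is broken.** The role is treated as unblinded as a precaution. The documents show a possible path for cues, not an actual disclosure.
- **That every AE and SAE is affected.** Section 10.7.1 permits that literal reading, but Section 8.3 and Appendix 3 point the other way.
- **That efficacy ratings are compromised.** PP-NRS is entered by the participant in an eDiary, and EASI is scored by a clinical evaluator. Section 10.7.4 changes neither. Leakage to raters is conceivable but not shown.
- **That two people share the SAE reporting clock.** The 24-hour limit for an SAE-associated deficiency runs from the investigator's awareness (8.3.9.3) or determination (10.7.6). The administrator/trainer has only a separate one-day limit for device deficiencies.
- **That the size of the trial measures the problem.** The numbers of participants and sites say how many people work under the instruction, not how many records it would touch.

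**Conclusion.** The point holds as an internal contradiction with a plausible but unquantified consequence for blinding. Section 10.7.4 conflicts with 6.1.1.2 and 6.4.2 on what the administrator/trainer may do, and with 8.3 and Appendix 3 on who reviews and records AEs and SAEs. The text conflict is certain, since it rests on the wording alone and survives the narrow device-only reading.

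The bias is less certain. It requires that an administrator/trainer notices the viscosity, forms a guess, and then lets it affect an entry or reach blinded staff. Exposure is greatest for syringe-related events, which this person is most likely to see. No rate of such events is given, so no number of affected records can be stated. The instruction should be corrected because the repair is cheap and the isolation rule has little value if an appendix overrides it. It is not a reason to doubt the primary or key secondary analyses.

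**What to change.** 1. In Section 10.7.4, assign documentation review and AE/SAE entry in the medical records and CRF to the investigator or a blinded designee. Change the bullet on sending copies of records in the same way.
2. Limit the administrator/trainer to physical facts about the syringe or device, reported by the IP Manual route that Sections 8.3.9.3 and 10.7.4 already cite, without access to clinical records. An adverse event that this person notices is handed to the investigator without comment on the product.
3. Add that single reporting duty to the permitted tasks in Sections 6.1.1.2 and 6.4.2, so that the isolation rule and the device duty agree.
4. Bring Sections 8.3.9 to 8.3.9.4 to the same split. Section 8.3.9.2 matters most, because its follow-up duty on the nature and cause of a deficiency would otherwise leave the conflict in place.
5. Align Section 6.1.2 with the same split and correct its pointer to Section 8.3.6.

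Editing 10.7.4 alone would not be enough. The cost is wording in several sections and a retraining note. No new role is needed, because the investigator already owns AE recording under Appendix 3. The one drawback is an extra hand-over when a device fault comes with an AE.

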10.7.5. Reporting of SAEs

- | SAE Reporting to Pfizer Safety via an Electronic Data Collection Tool |
|---|
| 
• The primary mechanism for reporting an SAE to Pfizer Safety will be the electronic data collection tool.• If the electronic system is unavailable, then the site will use the paper SAE data collection tool (see next section) in order to report the event within 24 hours.• The site will enter the SAE data into the electronic system as soon as the data become available.• After the study is completed at a given site, the electronic data collection tool will be taken off-line to prevent the entry of new data or changes to existing data.• If a site receives a report of a new SAE from a study participant or receives updated data on a previously reported SAE after the electronic data collection tool has been taken off-line, then the site can report this information on a paper SAE form (see next section) or to Pfizer Safety by telephone. |

- | SAE Reporting to Pfizer Safety via CT SAE Report Form |
|---|
| 
• Facsimile transmission of the CT SAE Report Form is the preferred method to transmit this information to Pfizer Safety.• In circumstances when the facsimile is not working, notification by telephone is acceptable with a copy of the CT SAE Report Form sent by overnight mail or courier service.• Initial notification via telephone does not replace the need for the investigator to complete and sign the CT SAE Report Form pages within the designated reporting time frames. |

